## 10. GRAPHICAL DATA SUMMARIES

1. Overall cohort accrual, including number of subjects screened, number excluded for each inclusion/exclusion criteria, and number of subjects per preoperative enrollment category will be presented graphically as a flow/consort diagram.
2. All ordinal endpoints will be plotted using stacked cumulative bar plots and cumulative probability plots.
3. All time-to-event endpoints will be plotted using Kaplan-Meier plots. Positive clinical event outcomes will be plotted as the cumulative rate of event, and negative events will be plotted as the cumulative rate of event-free.
4. All continuous endpoints will be plotted using histograms and boxplots.

5. All Bayesian logistic and frequentist logistic regression models will be plotted using forest plots.

## 11. DESCRIPTIVE STATISTICS

All demographics, baseline characteristics, and perioperative information will be summarized for all randomized participants, the ITT, and PPA analysis populations. Summaries will be presented by treatment group (metformin vs placebo), by treatment and dosage group, and by surgical strata. Data abstracted prospectively throughout the trial, data within trial reporting documentation, as well as data abstracted from the electronic health record will be recorded and included in the summaries. Baseline demographics and characteristics will include age at randomization, sex at birth, race, ethnicity, body mass index, frailty status as measured by the Risk Analysis Index, smoking status, Charlson Comorbidity Index, occurrence of comorbid conditions, preoperative medications, ASA class, surgical strata, and year of randomization. All analyses will be completed both in the ITT and PPA populations.

Primary and supplemental tables will include the following populations:

- 1- By primary treatment group (Metformin vs placebo)
- 2- By primary treatment group, separated by dose
- 3- By primary treatment group, separated by preoperative duration and dose
- 4- By surgical strata

All endpoints will be modeled following a standard convention based upon the frequency of the events. For interventions with <10 subjects, we will summarize outcomes with No. (%) without modeling due to the small sample size. All analysis will be completed both in the ITT and PPA populations.

- 1- Ordinal endpoints will be summarized by the number and cumulative frequency of each outcome. The 25th, 50th, and 75th percentiles will be summarized.
- 2- Dichotomous endpoints will be summarized by the proportion in each category.
- 3- Composite endpoints will be summarized overall and for each component individually.
- 4- Time-to-event outcomes will be summarized by the 2.5th, 10th, 25th, 50th, 75th, 90th, and 97.5th percentiles from the Kaplan-Meier estimates, as available.
- 5- Continuous endpoints will be summarized by the mean, standard deviation or median, interquartile range (IQR) pending the distribution of the data.

## 12. TREATMENT DELIVERY

Following randomization, study drug was either provided to the subjects in clinic or study drug was mailed directly to their home. Study drug compliance was monitored at the postoperative 90-day interaction with the study team. At this time, participants who discontinued their medications were determined not adherent and those who continued were adherent. In addition, if patients reported early termination or non-adherence to study drug, this was recorded by study coordinators and reported.

## 13. ANALYTIC APPROACH

Primary inferential analyses will be done using a Bayesian approach. Sensitivity analyses will be conducted using both Bayesian and Frequentist approaches, as described. Secondary endpoints will be analyzed using frequentist approaches. A summary of the analyses methods is provided below. For all frequentist models, statistical significance will be defined as a one-sided p-value of <0.025, and for all Bayesian models a one-sided posterior probability > 0.975. If stable inference cannot be made due to sparseness of data within strata/categories, data may be further collapsed as needed.

### 13.1. Primary Analysis of Primary Endpoint

#### *Primary Analysis*

The **primary analysis model** is a Bayesian cumulative logistic model for the ordinal primary endpoint. The primary analysis is to be completed in both the ITT and PPA populations described above.

In the primary analysis, observations will be pooled across pre-operative duration of study drug and will borrow across study drug dose. The primary endpoint for this model is HFD-90 and will be compared across the placebo and three levels of study drug dose. The general Bayesian cumulative logistic model is defined below:

Throughout we assume for patient  $i$ ,  $y_i$  is the observed 90-day HFD,  $g(i)$ , is the surgical strata from 1:G,  $d(i)$  is the pre-op duration from 1:3 with 1 = short, 2 = intermediate, and 3=long, and  $t(i)$  is the intervention from 1:4 with 1 = placebo, 2 = 500mg, 3 = 1000mg, and 4 = 1500mg.

The general Bayesian ordinal logistic regression model is used to estimate the effect of dose and duration of metformin on the distribution of HFD-90 under placebo adjusting for expected differences given the surgical strata. The ordinal scale parameterization is a generalized version of the dichotomous parameterization where we model all cumulative probabilities of 90-day HFD being less than or equal to a cutpoint  $c$ , where  $c = -1, \dots, 89$ . Given each cutpoint  $c$ , we denote the 91 dichotomized versions of 90-day HFD for patient  $i$  as  $\gamma_{c,i}$  where  $\gamma_{c,i} = 1$  if 90-day HFD is in  $[-1, c]$  and  $\gamma_{c,i} = 0$  if 90-day HFD is in  $[c+1, 90]$  for  $c = -1, \dots, 89$ .  $\gamma_{c,i}$  is then modeled throughout as:

$$\gamma_{c,i} \sim \text{Bernoulli}(\phi_{c,i});$$

$$\text{logit}(\phi_{c,i}) = \gamma_c + \mu_i;$$

where  $\mu_i$  is a patient-specific mean function and  $\gamma_c$  is common across all patients. To assure model stability, if there is an outcome in the ordinal scale that did not occur in the data, then that outcome will be combined with a neighboring outcome (the worse outcome). For example, if the outcome 11 never occurred, then a combined outcome of 10 & 11 will be modeled for the analysis.

The subject-specific mean function is as follows:

$$\mu_i = \alpha_{g(i)} + \theta_{t(i), d(i)}.$$

Within this model we assume that the underlying distribution of HFD-90 is different within each stratum,  $g$ , and these differences across strata can be explained by a proportional log-odds ratio shift in the HFD-90 distribution,  $\alpha_g$ . Stratum are defined in Section 7. Furthermore, we assume that the effects of each intervention within each pre-op duration are constant across strata and can be explained by a proportional log-odds ratio shift in the HFD-90 distribution  $\theta_{t,d}$ . Where a log-odds ratio  $\theta_{t,d} < 0$  results in an increase in expected HFD-90. For identifiability we assume the effect of placebo across all durations is zero,  $\theta_{1,d} = 0$  for all  $d = 1:3$ . As such, the values of the inverse logit of  $\gamma_c$  define the cumulative probabilities for each HFD-90 value under placebo, common across pre-op durations, and averaged across all strata. For all doses of metformin, we assume that the log-odds ratio of the effect of the dose is dependent on the pre-op duration and takes on the following form:

$$\theta_{t(i), d(i)} = \beta_t + \kappa_d \quad \text{for } t = 2, 3, 4 \text{ and } d = 1, 2, 3.$$

Here,  $\beta_t$  is the log-odds ratio due to the dose and  $\kappa_d$  is the log-odds ratio due to the duration. Under the primary analysis where we pool across all pre-op durations we assume  $\kappa_d = 0$  for all pre-op durations,  $d = 1:3$ .

The prior distribution of  $\gamma_c$  is specified on the probability scale:

$$\pi \sim \text{Dirichlet}(\alpha_1, \dots, \alpha_{90});$$

$$\gamma_c = \text{logit} \left( \sum_{i=-1}^c \pi_i \right);$$

With hyper-parameters,  $\alpha_h$ , specified based on the observed rates of HFD-90 across all strata in pre-trial data (discussed in Section 4) and providing 1 patient worth of information so that  $\sum_{h=1}^{90} \alpha_h = 1$ .

For the strata-specific log-odds ratios we place a normal prior distribution with mean 0 and standard deviation 2:

$$\alpha_g \sim N(0, 2^2).$$

Under the primary analysis, we assume a hierarchical distribution for the dose-effects centered around a common mean so there is borrowing of information across doses:

$$\beta_t \sim N(\mu_\beta, 5^2) \text{ for } t = 2, 3, 4;$$

$$\mu_\beta \sim N(0, 1).$$

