### **3. INTRODUCTION**

The population is aging. Over 50 million Americans are greater than 65 years of age. Associated with, but independent of aging, the cumulative effects of medical, social, and environmental stressors lead to frailty. The physiologic stress associated with the surgical treatment of disease is an age and frailty accelerating physiologic stressor, progressing frailty and further depleting resilience. As such, aging and frail patients, whom undergo over one third of all surgical interventions, have an increased risk of postoperative morbidity and mortality for all levels of physiologic surgical stress.

Strategies to Promote ResiliencY (SPRY) aimed to use the age and frailty inducing surgical intervention as an efficient experimental model to stabilize or even reduce frailty and the associated adverse postoperative outcomes. Using a randomized, embedded, multifactorial, adaptative platform (REMAP) trial strategy, we hypothesized that the pleiotropic and anti-inflammatory properties of metformin administered to non-diabetic patients in the perioperative period would reduce the age-accelerating physiologic stress as demonstrated through an increase in postoperative 90-day hospital free days (HFD) following an elective, major surgical intervention.

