### *Frequentist Sensitivity Analyses*

In addition, sensitivity analyses will be conducted in which frequentist regression models are used in place of the Bayesian cumulative logistic regression and without borrowing across groups. For these analyses, we will assess HFD-90 by 4 definitions of treatment arms based on the intervention, on both the ITT and PPA populations:

1. Treated (any duration and/or dose combined to a single group) vs. placebo
2. Metformin 1500mg ER vs. Metformin 1000mg ER vs. Metformin 500mg ER vs. Placebo (each pooled across duration)
3. Long Metformin (>90 days) vs. Medium Metformin (29-90 days) vs. Short Metformin (7-28 days) vs. Placebo (each pooled across the 3 doses of study drug)
4. Placebo vs. 500mg and 7-28 day duration vs. all other treatment combinations

For each of these definitions, we will apply two approaches:

1. A frequentist proportional odds model for the cumulative odds of 90-day HFD being less than or equal to a cut point  $c$ , where  $c = -1, \dots, 89$ , as described in the primary Bayesian analysis above. The treatment effect will be estimated, adjusting for surgical strata and duration as covariates.
2. A Mann-Whitney U test with ties for differences in HFD-90 by treatment arm. Test statistics and p-values will be presented. We will report death as a dichotomous outcome (vs. no death) and, among survivors, HFD-90 as a continuous outcome, as outlined in Section 11.

In the logistic regression model, the model structure will be as follows:

$$y_i = \text{logit}(\beta_0 + \beta_i * \text{tx arm}_i + \varepsilon_i);$$

Where:

$y_i$ : Outcome (HFD-90 = 90 vs.  $\neq 90$ ) for subject i

$\beta_0$  = Coefficient for intercept (for odds of outcome for placebo (reference) group)

$\beta_i$  = Coefficient(s) for treatment(s) vs. placebo

$\varepsilon_i$  = Residual Error for Subject I (i.e. Subject-level random/residual error)

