## 13.2. Analytic Approach for Secondary Endpoints

### *Primary Analysis*

The analysis of secondary endpoints will be conducted with Frequentist methods using unadjusted linear regression, logistic regression, and Cox models for continuous, dichotomous, and time-to-even secondary endpoints, respectively on both the ITT and PPA populations. Secondary endpoints are described in section 9.2 above. Treatment arms will be pooled across all durations and doses to form treated vs. placebo groups, with the placebo group used as the reference category in all analyses. There will be no adjustment for covariates, other than treatment arm.

The model structures will mimic the approach used in the frequentist analysis of the primary endpoint above. Specifically:

Linear regression:

$$y_i = \beta_0 + \beta_i * tx\_arm_i + \varepsilon_i;$$

Logistic regression:

$$y_i = \text{logit}(\beta_0 + \beta_i * tx\_arm_i + \varepsilon_i);$$

Cox Regression:

$$h(t|x_i) = h_0(t) * \exp(\beta_i * tx\_arm_i);$$

Where:

$y_i$  or  $h(t|x_i)$ : Secondary outcome of interest for subject  $i$

$\beta_0$  or  $h_0(t)$  = Coefficient for intercept or baseline hazard estimate

$\beta_i$  = Coefficient(s) for treatment(s) vs. placebo

$\varepsilon_i$  = Residual Error for Subject  $i$  (i.e. Subject-level random/residual error)

Statistical significance will be defined as an unadjusted  $p < 0.025$ . For all models, outputs will be reported using standard conventions and will include regression coefficients, standard deviations, confidence intervals, test statistics, and p-values, as relevant to each model. Model outputs will be reported both graphically and in tables, as described in sections 10 and 13.10.

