### **13.3. Subgroup Analyses**

For the primary outcome of HFD-90 only, subgroups will be evaluated using a frequentist cumulative logistic regression model, as in the primary analysis. These analyses will be conducted on both the ITT and PPA populations and will follow the same approach to pooling across duration and borrowing across dose as in the primary analysis. Analyses will be stratified by each of the following subgroups:

1. Age >= overall median vs < overall median (hypothesis, more effective among those > median)
2. Sex at birth (hypothesis: no difference)
3. Frailty, comparing robust/normal vs. frail/very frail (hypothesis, more effective among frail and very frail). Note that subgroup of robust with normal and frail with very frail may be modified as necessary (e.g., to robust vs. normal/frail/very frail) if sample size for either group is <= 25).
4. Surgical strata (hypothesis, no difference)
  - o No operation
  - o Spine
  - o General surgery/surgical oncology
  - o Colorectal Surgery
  - o Other
  - o Any strata with <= 25 subjects will be combined into the "Other" category, except the "No operation" group
5. Surgical stress (hypothesis, more effective among higher stress procedures)
  - o Same day surgery procedures
  - o Procedures with subsequent hospital admission

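### The primary HFD-90 model and its frequentist counterpart do not adjust for age or frailty, at a modest cost in precision whose size the documents cannot settle

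*SAP*

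**What the plan says.** SAP 13.1 specifies a Bayesian cumulative logistic model for HFD-90, "adjusting for expected differences given the surgical strata". The patient-level mean is a stratum effect plus a dose/duration effect, and the duration part is set to zero in the primary analysis. The frequentist proportional-odds model in the same section is fitted "adjusting for surgical strata and duration as covariates". For the secondary endpoints, section 13.2 states: "There will be no adjustment for covariates, other than treatment arm".

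Both omitted variables are listed in SAP section 11: "Baseline demographics and characteristics will include age at randomization", and the same list has "frailty status as measured by the Risk Analysis Index". SAP section 3 says that aging and frail patients "have an increased risk of postoperative morbidity and mortality for all levels of physiologic surgical stress".

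For HFD-90 the two variables appear only as subgroups in section 13.3: age as "Age >= overall median vs < overall median", and frailty in two groups. Neither document gives a reason for leaving them out of the models, or plans an analysis that adjusts for them.

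**The concern.** The introduction attributes extra risk to age and frailty at every level of surgical stress. That implies prognostic value beyond the type of operation, which is all that the primary model adjusts for. The early stop has also coarsened that one term: SAP section 4 reports that 14 surgical types were merged into 6 categories, so more case-mix variation may be left unexplained.

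In a proportional-odds model, omitting a prognostic covariate moves the treatment log-odds ratio towards zero, and the test statistic shrinks with it on average, even under randomization. Precision is what is at stake. The trial stopped before its first interval analysis at 500 patients, so further enrollment cannot recover it.

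**Working it through.** **No stated figure to reproduce.** The documents give no power, achieved sample size, HFD-90 distribution or prognostic strength. The numbers below are illustrations.

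**Inputs from the documents**
- Allocation √3:1:1:1 (SAP section 6), so the placebo share is r = √3/(√3+3) = 0.366.
- Clinically significant odds ratio 0.8 (Protocol 10.1).
- Posterior probability above 0.975 (SAP section 13), approximated as one-sided alpha 0.025.
- Fewer than 500 patients at the stop, inferred from SAP section 4.

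**Assumed inputs**
- N = 400 as the main case.
- Σp³ between 0.01 and 0.10 for the HFD-90 distribution.
- One standardized score standing for age plus frailty, with log-odds SD 0, 0.3, 0.6 or 1.0 beyond stratum. With the logistic residual variance of 3.29, the share of latent variance is SD²/(SD²+3.29): 0.09/3.38 = 3%, 0.36/3.65 = 10% and 1/4.29 = 23% for the last three.

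**Step 1. Background power without the covariates** (pooled metformin vs placebo)

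Information V = N·r(1−r)·(1−Σp³)/3, and power = Φ(|log OR|·√V − 1.96).

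For N = 400 and Σp³ = 0.05: V = 400 × 0.2320 × 0.3167 = 29.4, √V = 5.42, and 0.2231 × 5.42 = 1.21. Power = Φ(−0.75) = 23%.

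Over the Σp³ range:

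| N | Power at OR 0.8 |
|---|---|
| 200 | 13–14% |
| 400 | 22–23% |
| 500 | 26–28% |
| 2000 | 75–79% |
| 2500 | 84–87% |

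**Step 2. Simulation with and without the score**

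There were 600 replicates per setting, with an assumed 10-category outcome and six strata in both models. The Monte Carlo standard error is about 2 points for each power.

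| N | OR | Score SD | Power, strata only | Power, strata + score | Mean log-OR, strata only / adjusted |
|---|---|---|---|---|---|
| 400 | 0.8 | 0 | 25.2% | 25.2% | −0.216 / −0.217 |
| 400 | 0.8 | 0.3 | 21.3% | 21.5% | −0.216 / −0.222 |
| 400 | 0.8 | 0.6 | 22.3% | 22.5% | −0.210 / −0.226 |
| 400 | 0.8 | 1.0 | 17.3% | 22.0% | −0.187 / −0.225 |
| 400 | 0.6 (assumed) | 0.3 | 74.7% | 75.7% | −0.500 / −0.511 |
| 400 | 0.6 (assumed) | 0.6 | 71.7% | 77.8% | −0.477 / −0.507 |
| 400 | 0.6 (assumed) | 1.0 | 65.8% | 81.3% | −0.446 / −0.535 |
| 500 | 0.6 (assumed) | 0.6 | 83.5% | 86.7% | −0.477 / −0.515 |

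The true log-odds ratios are −0.223 (OR 0.8) and −0.511 (OR 0.6). Shrinkage shows clearly at SD 0.6 and 1.0.

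**Step 3. Cross-check**

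A second simulation (500 trials per scenario, N = 400, assumed OR 0.65, no stratum term described) put the value of adjustment at 5%, 13% or 28% more patients when the covariates explain 5%, 10% or 20% of latent variance. Multiplying V in Step 1 by 1.05, 1.13 and 1.28 at OR 0.8 changes 1.21 to 1.24, 1.29 and 1.37. Power goes from 23% to 24%, 25% and 28%. These gains of roughly 1, 2 and 5 points agree with Step 2 within its simulation error.

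**Limit.** Both simulations are frequentist comparisons of pooled metformin with placebo. They do not reproduce the three-dose Bayesian model with borrowing.

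**The case against.** The strongest reply is that this is a defensible choice. SAP section 4 says the model was prespecified before enrollment. The changes to strata and durations were forced by the early stop, and adding prognostic terms is a different kind of change. That argues for caution about replacing the primary model. It does not argue against a named supportive analysis.

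Other parts of the reply limit the point:

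- **Strength of prediction.** The SAP gives no effect size for age or frailty on HFD-90. Eligibility (age 60 or over, or younger with a Charlson index above 2) may narrow the spread of age and makes a straight-line age effect doubtful.
- **Availability.** A reader might infer that both variables are recorded for everyone. Section 11 only lists them for summary, partly from health-record abstraction. Section 13.5 expects missing covariates and fills them with the median within dose. Missing index scores would reduce the gain.
- **Timing.** A reader might infer that adding covariates is free of selection risk. That holds only under blinding. Section 1.1 dates the SAP's finalization to 06 September 2023, and section 5 holds unblinding only until then. The documents do not show whether the window is still open.
- **Bias.** A reader might take the shrunken odds ratio as confounding. Treatment is randomized, so it is not. Part of the shift is non-collapsibility: the strata-only and adjusted odds ratios are different estimands. The per-protocol set is selected on reported completion of study drug. That is a separate problem, which two covariates would not solve.

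**Conclusion.** The point holds as a modest efficiency loss. The direction is secure if age and frailty predict HFD-90 beyond stratum, as the SAP's rationale implies. The size is not secure. At an assumed N of 400 and odds ratio 0.8, the simulated gain is about 0 to 1 point for log-odds SD 0.3 to 0.6 (up to about 2 points on the cross-check) and about 5 points for SD 1.0. Gains of about 6 to 15 points appear only with an assumed odds ratio near 0.6 and SD 0.6 to 1.0.

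A reader might infer that adjustment would rescue the trial's power. It would not: with the illustrated gains, power at odds ratio 0.8 and N = 400 stays below 30%. The early stop is the main cause. Nothing here questions the validity of the randomized comparison or its type I error.

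**What to change.** While treatment is still blinded, add two terms to the mean function in SAP 13.1 and to the frequentist proportional-odds model:

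- Age, allowing a non-linear form, because patients under 60 enter only with comorbidity.
- Risk Analysis Index score.

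Give both weakly informative normal priors in the Bayesian model. If the model prespecified before enrollment stays primary, name the covariate-adjusted version as the key supportive analysis. Label its odds ratio as conditional on stratum, age and frailty, and report how many index scores are missing and imputed. If unblinding has already taken place, label the adjusted analysis as added later and report it under the exploratory rules of section 13.4.

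The cost is a short SAP amendment and a few model terms. The downside is a small departure from the prespecified model, or one extra analysis to report.

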8.3.4. Duration of Administration of Study Drug

The duration of Metformin therapy is a complimentary research question in this domain. In the short course intervention, subjects will receive the study drug (metformin or placebo) within 7-28 days prior to the elective surgical encounter. In the intermediate course therapy, subjects will receive the study drug for 29-90 days prior to surgery. In the long course therapy, patients receive a longer course of study drug prior to surgery when the pre-operative evaluation occurs far enough in advance (e.g., >3 month). All patients will receive study drug for 90 days after the surgical encounter.

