## **6. INTERVENTIONS**

There is one active intervention and one control within this analysis plan:

- 1- Metformin
- 2- Placebo

Preoperative duration of study drug was pragmatically chosen based upon the time interval between the time of enrollment and scheduled operating room date including:

- 1- Short – 7-28 days
- 2- Medium – 29-90 days
- 3- Long – >90 days

Preoperative duration is not considered in the primary model but was considered in planned sensitivity analyses. Patients were randomly assigned,  $\sqrt{3}$ :1:1:1 to placebo and the 3 doses of metformin:

- 1- Placebo
- 2- Metformin 500mg ER
- 3- Metformin 1000mg ER
- 4- Metformin 1500mg ER

The dosing of and route of administration of metformin guidance included to take an oral dose once daily and complete all dispensed medication from the provided pill bottle.

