### Bayesian Sensitivity Analyses

Sensitivity analyses will be conducted in both ITT and PPA populations to assess alternative definitions to degree of study drug exposure. Specifically, the Bayesian cumulative logistic regression with HFD-90 outcome and analysis populations will be conducted for pooling across study drug dose and borrowing across pre-operative duration of study drug. The Bayesian ordinal logistic model will be the same as described above except with the following modifications to  $\theta_{t,d}$

$$\theta_{t(j),d(j)} = \beta_t + \kappa_d \quad for \ t = 2,3,4 \ and \ d = 1,2,3.$$

Here,  $\beta_t$  is the log-odds ratio due to the dose and  $\kappa_d$  is the log-odds ratio due to the duration. Under the sensitivity analysis where we pool across all active doses we assume  $\beta_t = 0$  for all active doses,  $t = 2:4$ .

Under the sensitivity analysis, we assume a hierarchical distribution for the pre-op duration effects centered around a common mean so there is borrowing of information across pre-op durations:

$$\kappa_d \sim N(\mu_k, .5^2) \text{ for } d = 1,2,3;$$

$$\mu_k \sim N(0,1).$$

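### The duration analyses compare each metformin duration with placebo patients of every duration, so prognosis by waiting time can be read as a metformin duration effect

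*SAP*

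**What the plan says.** **Duration is not randomised.** SAP section 6: "Preoperative duration of study drug was pragmatically chosen based upon the time interval between the time of enrollment and scheduled operating room date". Protocol section 7 likewise leaves it to the patient's clinical course. Only dose is randomised, √3:1:1:1.

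**Placebo patients have a duration too.** In Protocol 8.3.4, for the short course, "subjects will receive the study drug (metformin or placebo) within 7-28 days prior to the elective surgical encounter". In SAP 13.1, d(i) "is the pre-op duration from 1:3 with 1 = short, 2 = intermediate, and 3=long", defined for every patient.

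**The Bayesian model ignores it for placebo.** The mean is μ_i = α_g + θ_{t,d}, with surgical stratum as the only covariate. SAP 13.1 then states: "For identifiability we assume the effect of placebo across all durations is zero". The placebo distribution is described as "common across pre-op durations, and averaged across all strata". The duration sensitivity model is specified as "pooling across study drug dose and borrowing across pre-operative duration of study drug". It sets the dose effects to zero and gives metformin patients κ_d ~ N(μ_κ, 0.5²) with μ_κ ~ N(0, 1); everything else carries over. The success rule in SAP section 13 is "for all Bayesian models a one-sided posterior probability > 0.975".

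**Other duration analyses.** Treatment definition 3 in the frequentist sensitivity analyses sets long, medium and short metformin against one placebo group. The proportional-odds model adjusts for stratum and duration; the Mann-Whitney test adjusts for nothing. SAP 13.2 uses the same arms for secondary endpoints, with treatment arm as the only model term.

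**The primary analysis is separate.** SAP section 6: "Preoperative duration is not considered in the primary model but was considered in planned sensitivity analyses".

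**The concern.** How long a patient waits for an operation may well be related to how that patient will do. If it is, comparing long-wait metformin patients with placebo patients of all waits mixes prognosis with drug effect. Randomisation protects the comparison of metformin with placebo within a duration, but not this one.

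Protocol section 7 hypothesises that a longer course gives more hospital-free days, and the 0.975 threshold lets the Bayesian duration effects be declared positive. For HFD-90, the proportional-odds model is presented as the Bayesian analysis without borrowing, but for duration the comparator changes as well. If the two disagree, the results alone do not separate the effect of borrowing from that of the comparator. For secondary endpoints by duration, no adjusted version is planned.

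**Working it through.** The plan gives no figure on this point to reproduce. The check is the algebra of the contrast, then its size under stated assumptions.

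**Which contrast is estimated.** Suppose metformin does nothing and, within stratum, the log-odds of a worse outcome shift by δ_d with waiting time. Let p_d be the share of patients with duration d. Metformin patients at duration d sit at δ_d; the single placebo reference sits at about Σ p_d δ_d. So in large samples

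κ_d → δ_d − Σ p_d δ_d,

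which is zero only if prognosis does not vary with waiting time within strata. In the unadjusted analyses, prognostic differences between strata enter as well.

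**Inputs.**
- From the SAP: allocation √3:1:1:1, so the placebo share is √3/(√3+3) = 0.366; the κ prior; the 0.975 threshold; one-sided 0.025 for frequentist tests.
- Assumed: N = 400 (the trial stopped before its first interval analysis, set at 500 enrolled); duration mix 50/35/15%; intermediate waiters midway in prognosis; w = 0.2 to 0.3 units of information per patient; inert drug.
- Resulting cells: about 146 placebo patients, of whom 22 are long-wait (146 × 0.15), and about 38 long-wait metformin patients (254 × 0.15).

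**Bias.** Let L = ln(OR), where OR compares long with short waiters, long waiters being better. Then δ = (0, −L/2, −L), the weighted mean is −(0.35 × 0.5 + 0.15)L = −0.325L, and κ_long → −0.675L. For OR 1.5: −0.675 × 0.405 = −0.274, an apparent odds ratio of 0.76.

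**False claims that long metformin beats placebo, base case.** The Bayesian figures use a closed-form normal approximation: six cell means with variance 1/(w·n), combined with the SAP prior. The Mann-Whitney figures come from 6,000 simulated trials per setting, with 2% deaths and either 18% or 70% of patients at 90 days; there the OR includes differences between strata.

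| Long vs short wait OR | Apparent OR, metformin-long | Bayesian | Mann-Whitney |
|---|---|---|---|
| 1.0 | 1.00 | 1.4-1.6% | 2.5% (nominal) |
| 1.25 | 0.86 | 3.1-4.4% | 4.8-7.0% |
| 1.5 | 0.76 | 5.6-8.7% | 8.4-13.0% |
| 2.0 | 0.63 | 12.3-20.7% | 15.2-29.6% |

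**Other settings at OR 1.5, Bayesian long arm.** N = 200: 2.5-4.0%. N = 499: 7.1-10.9%. Equal thirds: 7.1-10.1%. With a 70/25/5% mix the long arm is at about 2-3%, but the intermediate arm reaches 4.4-5.8%.

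**If long waiters do worse.** Short metformin is falsely favoured in 5.5-7.2% (OR 1.5) or 9.8-14.2% (OR 2.0) with the Bayesian model, and in 7.6-9.4% or 15.2-17.8% with Mann-Whitney. In the Bayesian model the long-arm claim rate falls to 0.2% or less, which would mask a real benefit.

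**Long against short.** The SAP sets no rule for this contrast. Read at 0.975, it would give false claims in 9.9-16.7% (OR 1.5) or 28.3-46.1% (OR 2.0).

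**With a shared duration term, base case.** Long-over-placebo 0.4-0.8% and short-over-placebo 1.4-1.9%, at every OR in the table. Mann-Whitney against same-duration placebo gives 2.2-3.2% in every setting.

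**Second method.** Ordinal data were simulated with six strata and fitted by maximum-likelihood proportional odds combined with the SAP prior (300 runs per case, N = 400). With shifts of +0.3, 0 and −0.3 for short, medium and long waits (OR e^0.6 ≈ 1.8), mean κ_long was −0.34 with 18% false claims; Mann-Whitney gave 25%. A shared duration term brought mean κ to within 0.03 of zero in every case. When prognosis differed only through strata, the Bayesian κ stayed near zero, but Mann-Whitney still rejected in 8-9% for medium and long.

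**The case against.** The strongest reply concerns weight. No primary inference is touched: the primary model sets every κ_d to zero and compares randomised doses. For the endpoint of the duration hypothesis, a duration-adjusted proportional-odds model is already planned. The common-placebo assumption is written in the SAP, not hidden. With few long-wait placebo patients, sharing all placebo patients is a defensible trade of bias for precision. All of this stands; it limits the severity but does not make the contrast a same-duration one.

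The size also rests on assumptions, and under modest confounding the long-arm Bayesian rate is not above nominal: 1.6-2.4% at OR 1.25 with N = 200, and 1.0-1.7% at OR 1.25 with the 70/25/5% mix. That too stands.

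On identifiability, one placebo level does have to be fixed because the cutpoints are free. The other two zeros are not needed, since placebo patients are observed at each duration.

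The point also reaches further than the three analyses named. Treatment definition 4 (500 mg short course against all placebo) and the logistic model for HFD-90 = 90, which contains treatment arm only, have the same comparator. SAP 13.1 does not say which pairs the Mann-Whitney test compares; each duration arm against all placebo is the natural reading. The tables by treatment group, duration and dose in SAP section 11 may show placebo outcomes by wait, but they do not correct the estimates.

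**Conclusion.** The concern holds. In the Bayesian duration model, the Mann-Whitney test by duration arm and the secondary-endpoint duration comparisons, the reference is placebo of all durations, so any prognostic gradient with waiting time enters the metformin duration effect. In the Bayesian model only the part not explained by surgical stratum enters; in the other two all of it does.

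Direction and size are unknown, because the documents give no final N, duration mix or prognosis by wait. Under the base-case assumptions, the false-claim rate for long metformin rises from about 1.5% to 5.6-8.7% at OR 1.5. It is near nominal when the trial is small or long waits are rare, and there is no bias if residual prognosis does not vary by wait. The trial's main conclusion does not depend on these analyses, so this should be corrected but does not threaten the primary result.

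**What to change.** 1. In the Bayesian duration model use μ_i = α_g + δ_d + θ, with δ_d shared by placebo and metformin, one level fixed at zero and N(0, 2²) priors on the other two. κ_d is then metformin against placebo within duration d, the contrast the proportional-odds model already estimates.
2. Run the Mann-Whitney duration comparisons against placebo of the same duration.
3. Add duration as a covariate to the secondary-endpoint duration comparisons. Treat definition 4 and the HFD-90 = 90 logistic model in the same way.
4. Where a same-duration placebo group has fewer than 10 patients, summarise without modelling. This extends the small-group rule in SAP section 11, which is written for interventions.
5. Label any long-versus-short statement as effect modification by a non-randomised characteristic. The common-placebo version may be reported alongside, with its assumption stated.

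The cost is two parameters and SAP wording; there are no new data and no change to the primary analysis. The price is precision. In the base case the posterior SD for long metformin rises from 0.30-0.36 to 0.38-0.43, for short from 0.22-0.26 to 0.25-0.29, and for long minus short from 0.30-0.35 to 0.43-0.48. With the 70/25/5% mix (about 7 long-wait placebo patients) the SD for long rises from 0.42-0.47 to 0.50-0.54. The adjusted proportional-odds model pays a similar price: the SE of the long-arm log odds ratio is √(1/(w·38) + 1/(w·22)) = 0.49-0.60, against √(1/(w·38) + 1/(w·146)) = 0.33-0.41 with all placebo.
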